2. SCIENTIFIC COMPONENT, METHODOLOGY, ETHICS, AND PLANNING

2.1 RESEARCH QUESTION AND HYPOTHESIS

Research Question: What is the efficacy of a personalized concurrent exercise prescription guide combined with pharmacological treatment, compared to pharmacological treatment alone, in controlling cardiovascular risk factors and physical capacity in adult users of the Cardiovascular Health Program at CESFAM Externo de Valdivia during 2024?

Hypothesis:

- **H1:** The efficacy of a personalized concurrent exercise prescription guide combined with pharmacological treatment is greater than pharmacological treatment alone in controlling CRF and physical capacity in adult users of the Cardiovascular Health Program at CESFAM Externo de Valdivia during 2024. (hypothesis of group difference)
- **H0:** The efficacy of a personalized concurrent exercise prescription guide combined with pharmacological treatment is equal to pharmacological treatment alone in controlling CRF and physical capacity in adult users of the Cardiovascular Health Program at CESFAM Externo de Valdivia during 2024. (hypothesis of group difference)

Statistical Hypothesis:

- **Group Difference Hypothesis:**
 - **H0:** $\mu_A = \mu_B$
 - **H1:** $\mu_A > \mu_B$

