2.3 METHODOLOGY AND PROCEDURES

Research Design: The research design corresponds to a Pilot Randomized Controlled Trial (RCT), with parallel groups and superiority. The design aligns with the general objective and proposed hypothesis as it will evaluate the efficacy of a personalized concurrent exercise prescription guide combined with pharmacological treatment, compared to pharmacological treatment alone, in controlling cardiovascular risk factors and physical capacity.

Study Variables: Primary variables include the standard CHP control parameters: blood pressure, fasting glucose, total cholesterol, and triglycerides. Secondary variables include sociodemographic and medical background, physical activity level, muscular strength, cardiorespiratory capacity, body composition, adherence to the exercise guide, and patient perception of changes due to the intervention.

Population: The population will consist of adult users of the CHP registered at CESFAM Externo de Valdivia. The research team will invite users directly during their regular controls at CESFAM Externo. The research team, identified as staff from Universidad San Sebastián, will provide detailed information about the study, the exercise prescription guide, program duration, benefits, and risks in a designated space. Interested individuals will be asked to sign an informed consent form. The recruitment period will be necessary to obtain the total sample, with a maximum of 1 month. If the sample is not obtained within this period, recruitment will be extended by 1 month.

Selection Criteria: Inclusion:

- Physically inactive (not engaging in 300 or 150 min. of moderate or vigorous physical activity per week, respectively, measured with the IPAQ questionnaire)
- Body mass index (BMI) between 25 and 39.9 kg/m²
- Registered in the Cardiovascular Health Program

- Diagnosis of Hypertension with the use of 1 and/or 2 antihypertensive medications
- Diagnosis of Type 2 Diabetes Mellitus with the use of 1 oral hypoglycemic, non-insulin-dependent
- Diagnosis of Dyslipidemia with the use of 1 lipid-lowering medication
- Having a phone device

Exclusion:

- Bone disease
- Ischemic disease or arrhythmia
- Chronic respiratory disease
- Uncontrolled chronic diseases
- Inability to provide informed consent or comply with tests and exercise protocol for any reason
- History of oncological disease or undergoing investigation for suspected neoplastic disease
- Female participants who are pregnant

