Sample Size Calculation: The sample size calculation will be based on literature recommendations for pilot studies and includes:

1. T-test – Means: difference between two independent means
2. Type I error: 5%
3. Statistical power: 80%
4. Effect size (ES): 0.5 according to Cohen's classification. Using these parameters, the recommended total sample size is 15 subjects per group. Assuming a 30% dropout rate, the total population will be 39 participants. After the eligibility process, participants will be randomly assigned to an experimental group (EG) and a control group (CG) using a 1:1 ratio online system (<https://www.randomizer.org/>). Assignment concealment will be carried out by an investigator not involved in the clinical procedures of the RCT using opaque, sealed, and consecutively numbered envelopes. The random sequence and assignment concealment will control selection bias.

The experimental group will receive the intervention based on the personalized exercise prescription guide plus their usual pharmacological treatment associated with the CHP, and the control group will maintain their usual pharmacological treatment associated with the CHP.

Data Collection Techniques: All evaluations will be conducted pre- and post-intervention in the experimental and control groups.

Clinical Record Information Review: The CHP medical manager, with authorization from the CESFAM Externo management and approval from the Ethics Committee of the Valdivia Health Service, will review the clinical records of participants, gathering the following information:

- Sociodemographic and medical background: sex, age, education level, duration in the cardiovascular health program, comorbidities, medications, dosage, and duration of medication use. These variables will be used to characterize the study sample.

Cardiovascular Risk Factor Evaluation: Evaluations and user follow-up will be conducted by physical therapists trained in evaluation techniques, exercise prescription, and cardiovascular risk factors, at the Universidad San Sebastián Health Center located at [name], Valdivia. A physical therapist will measure variables and be blinded to the participant's intervention assignment.

Cardiovascular Variables Evaluation: Blood pressure (systolic and diastolic) and heart rate will be measured using an automatic monitor (Omron HEM 7130™) following the standard procedure in a seated position after 15 minutes of rest, conducted before and after the intervention.

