Aerobic Exercise: Participants will perform 5-10 intervals/session of walking or jogging at moderate to high intensity, with a rating of 5 to 8 points on the modified Borg scale (1-10 points). Each interval will consist of 1 minute of walking or jogging, followed by 2 minutes of inactive rest. Every 2 weeks, the load (cadence) will be adjusted due to normal physiological adaptations, always exercising at an intensity of 5-8 points on the modified Borg scale, similar to previous studies.

Muscular Resistance Exercise: Participants will perform concentric, eccentric, and/or isometric contractions for 1 minute at an intensity of 5-10 according to the OMNI-RES scale. The rest period will last 2 minutes, and each exercise will be repeated 3 times. Three exercises will be performed per session: squats, push-ups, and planks. Exercise difficulty (load) will be adjusted according to the user's abilities. The exercise load may be modified every two weeks according to the physiological adaptations of

the subjects, to adjust the loads to the new thresholds, always working at an intensity of 5-10 on the OMNI-RES scale.

Pharmacological Treatment: Participants will be asked to maintain their lifestyle, including taking prescribed medications as usual.

Participants will be asked to complete a "control diary" with the sessions and exercises performed during the intervention, noting any medication changes, illnesses, and additional physical activity.

Control Group: Pharmacological treatment.

Participants in the control group will be asked to maintain their current lifestyle and exercise habits throughout the study, including taking prescribed medications as usual. They will complete a "control diary" to note any exercise, medication changes, illnesses, and relevant information. Once control participants complete post-intervention evaluations, they will be offered the opportunity to complete the same intervention as the exercise group.

Statistical Analysis: In this study, dependent variables will be described using mean and standard deviation. Normality and homoscedasticity assumptions will be verified using the Shapiro-Wilk test for all data.

To identify group differences at baseline and post-intervention, the Student's t-test for independent samples will be used, complemented by Levene's test for variance comparison between groups.

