A two-way repeated measures ANOVA will be used to determine intra-group and inter-group differences. Model effects will include Group (CG and EG), Time (Pre-test, Post-test), and their interaction over time (Group x Time). Tukey's post hoc test will be used for variables with Group \times Time interaction. Data analysis will be conducted by an investigator blinded to the intervention groups. Intention-to-treat analysis will be considered using the multiple imputation method for handling missing data and incomplete datasets.

The clinical significance of the interventions will be determined by effect size using Cohen's "d" (<0.2 =negligible, $0.2-0.49$ =small, $0.5-0.79$ =moderate, ≥ 0.8 =large). The clinical relevance of interventions will be assessed based on perceived therapeutic changes by participants using the Global Rating Scale (GRS). The GRS will evaluate the intervention's impact on relevant domains from the user's perspective and experience, using a 15-point Likert scale (-7=much worse, 0=no change, +7=much better). Differences interpretation: 1-3 points=small, 4-5=moderate, 6-7=significant.

All statistical analyses will be conducted using SPSS version 26 (SPSS™ Inc., Chicago, IL, USA).

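### Two between-group tests are planned for each outcome and neither is named as deciding efficacy; one baseline-adjusted ANCOVA per outcome should be named

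*Combined protocol and SAP*

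**What the plan says.** Section 2.1 states a directional efficacy hypothesis: exercise guide plus drugs "is greater than pharmacological treatment alone in controlling CRF and physical capacity in adult users". Section 2.3 calls the design a pilot and also a superiority trial: "The research design corresponds to a Pilot Randomized Controlled Trial (RCT), with parallel groups and superiority". Under Study Variables, "Primary variables include the standard CHP control parameters: blood pressure, fasting glucose, total cholesterol, and triglycerides". Under Data Collection Techniques, "All evaluations will be conducted pre- and post-intervention in the experimental and control groups", so a baseline value is planned for each of these variables.

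The Statistical Analysis part then assigns two procedures to differences between the arms:

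- "To identify group differences at baseline and post-intervention, the Student's t-test for independent samples will be used", with Levene's test alongside.
- "A two-way repeated measures ANOVA will be used to determine intra-group and inter-group differences". Its terms are arm, visit and the interaction of the two.

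A follow-up step applies only where that interaction appears; the sentence begins "Tukey's post hoc test will be used for variables with Group". No sentence ranks these procedures, says which one tests the hypothesis, or says what happens if they disagree. Baseline is not used as a covariate anywhere.

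**The concern.** A single efficacy hypothesis needs a single deciding result for each outcome. The plan produces at least two, the post-only t-test and Group x Time. The ANOVA also yields a Group main effect, which averages in the pre-treatment value and is not a clean efficacy test.

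The indirect clues point in different directions. The Tukey step depends on the interaction, which suggests that Group x Time is the gate. The sample size calculation uses a test of two independent means, which suggests the post-only comparison. If the two p-values fall on opposite sides of 5%, the choice between them would be made after both are seen. Blinding the analyst to group labels does not prevent that.

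There is also an efficiency loss. The post-only test ignores the baseline values. Group x Time subtracts them in full however weakly they predict the post value.

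**Working it through.** **Inputs from section 2.3:** 15 per group, effect size d = 0.5, type I error 5%, power 80%, 30% dropout, 39 in total.

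**Assumptions, because the documents do not give them:** pre-post correlation r (0.3, 0.5 and 0.7 shown, extremes noted), sidedness of the tests (section 2.1 writes mu_A > mu_B but the tests' sidedness is not stated), normal data, equal SD before and after.

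**The plan's own figure.** For a two-sample t-test at d = 0.5, n per arm = 2(1.96 + 0.84)²/0.5² ≈ 63 (64 by the exact t calculation; 50 or 51 one-sided). The stated 15 per group does not follow from these inputs. That is a separate matter. Here 15 is taken as the number the plan intends to have at the end.

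**Step 1: the two planned estimates.** Let D_pre and D_post be the between-arm differences in means.

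- The post-only t-test estimates D_post.
- Group x Time with two time points estimates D_post − D_pre.
- The gap between them is D_pre, which is pure chance under randomisation.
- SD of D_pre = √(2/15) = 0.365 outcome SDs.
- P(|D_pre| > 0.5) = P(|Z| > 0.5/0.365) = P(|Z| > 1.37) ≈ 17%.

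**Step 2: relative variance, with post-only set to 1.** Group x Time is 2(1 − r). ANCOVA in large samples is 1 − r².

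| r | Post-only | Group x Time | ANCOVA |
|---|---|---|---|
| 0.3 | 1 | 1.40 | 0.91 |
| 0.5 | 1 | 1.00 | 0.75 |
| 0.7 | 1 | 0.60 | 0.51 |

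The two planned tests change places at r = 0.5. ANCOVA is below post-only because r² > 0, and below Group x Time because 2(1 − r) − (1 − r²) = (1 − r)² > 0. This holds for every r between 0 and 1.

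**Step 3: simulation at 15 per arm, d = 0.5, 100,000 trials per setting.** Each cell gives post-only / Group x Time / ANCOVA.

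| r | Power, two-sided 5% | Power, one-sided 5% | Mean 95% CI half-width (SD) | Planned tests disagree (two-sided) |
|---|---|---|---|---|
| 0.3 | 27 / 20 / 28% | 38 / 31 / 40% | 0.74 / 0.88 / 0.72 | 23% |
| 0.5 | 26 / 26 / 32% | 38 / 38 / 45% | 0.74 / 0.74 / 0.65 | 27% |
| 0.7 | 26 / 40 / 44% | 38 / 53 / 58% | 0.74 / 0.57 / 0.54 | 36% |

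Repeat runs agree within about one percentage point. Two-sided, ANCOVA gains about 1 to 6 points over the better planned test and 6 to 18 over the worse one.

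**Step 4: no true effect.** Each of the three tests alone rejects in about 5% of trials. At least one of the two planned tests rejects in about 9% (8.8% to 9.5% for r from 0.3 to 0.8). This figure would apply only if either result were accepted as success, a rule the plan does not state.

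**The case against.** The strongest reply is that the defect is only the missing label. Each planned test is valid at 5%, and naming Group x Time alone would also settle which result decides. ANCOVA is then an efficiency gain, and at high correlation a negligible one: at r = 0.9 power is 84.1% for Group x Time and 84.4% for ANCOVA. All of this is correct. What remains is that choosing either planned test means guessing r, while ANCOVA does not.

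Two numerical limits also stand.

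- The variance ordering is a large-sample result. At 15 per arm and r = 0.1, power is 26.2% post-only against 25.7% for ANCOVA, and at r = 0.2 they are level. The loss is at most about half a point.
- The 15-per-arm figures describe completers. If all 39 were analysed (19 and 20), the baseline gap would have SD √(1/19 + 1/20) = 0.32 and would exceed 0.5 SD in about 12% of trials rather than 17%.

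The trial is a pilot, and section 2.2.2 sets partly descriptive aims. That softens the need for a decision rule but does not remove it, since sections 2.1 and 2.3 state an efficacy hypothesis and a superiority design.

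Tukey contrasts could still describe within-arm change. As a test of the treatment effect they add nothing to an interaction with one degree of freedom.

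**Conclusion.** The concern holds. The plan gives two different estimates of the treatment effect for each outcome, does not say which decides, and makes no covariate use of the baseline values it collects. At 15 per arm and a true effect of 0.5 SD, the two planned tests would give different verdicts in roughly a quarter to a third of trials for r between 0.3 and 0.7. ANCOVA had the highest power of the three at each of these correlations. These sizes rest on the assumed r, normality and equal SDs.

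This is a change that should be made, but it does not invalidate the trial, because each planned test is sound alone. It leaves two problems untouched: two-sided power stays at 28% to 44% for r from 0.3 to 0.7, and several variables remain jointly primary.

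**What to change.** In the Statistical Analysis part of section 2.3:

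1. Name one efficacy analysis for each continuous outcome measured at both visits: linear regression (ANCOVA) of the post value on group, adjusted for the baseline value of the same variable. Report the adjusted mean difference with its 95% CI, and state whether the test is one- or two-sided.
2. Label the post-only t-test and the repeated-measures ANOVA, including its Group main effect, as secondary or descriptive.
3. Drop Tukey as a test of the treatment effect.
4. Describe baseline by arm without significance tests. Under randomisation any difference is chance, and such a test should not steer the choice of analysis.
5. If multiple imputation is kept, say that this same model is fitted in each imputed data set and the results pooled.

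The cost is a few sentences and one degree of freedom per model. No new data are needed, and the model runs in the software already named. If the investigators prefer Group x Time, one sentence naming it as the deciding test would remove the ambiguity, at the loss of precision shown above.

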2.2.2 SPECIFIC OBJECTIVES

- Describe the effects of applying a personalized concurrent exercise prescription guide on cardiovascular risk factors in adult users of the Cardiovascular Health Program at CESFAM Externo de Valdivia.

- Describe the effects of applying a personalized concurrent exercise prescription guide on physical capacity in adult users of the Cardiovascular Health Program at CESFAM Externo de Valdivia.
- Evaluate adherence to the personalized concurrent exercise guide and pharmacological treatment in adult users of the Cardiovascular Health Program at CESFAM Externo de Valdivia.
- Describe the clinical significance of interventions through effect size calculation and perceived clinical relevance by participants regarding the interventions.

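### The plan does not say which of its between-arm results decides efficacy; Group × Time estimates the full effect, the Group main effect half of it, and the Time main effect pools both arms

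*Combined protocol and SAP*

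**What the plan says.** The Statistical Analysis part of section 2.3 plans two sets of comparisons for the same variables.

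- A t-test at each time point: "To identify group differences at baseline and post-intervention, the Student's t-test for independent samples will be used".
- An ANOVA with a double purpose: "A two-way repeated measures ANOVA will be used to determine intra-group and inter-group differences". Its terms are listed: "Model effects will include Group (CG and EG), Time (Pre-test, Post-test), and their interaction over time (Group x Time"). Follow-up testing depends on the interaction: "Tukey's post hoc test will be used for variables with Group" × Time interaction.

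There is one measurement before and one after: "All evaluations will be conducted pre- and post-intervention in the experimental and control groups".

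The general objective (2.2.1) and the hypotheses (2.1) compare guide plus drugs with drugs alone. Specific objectives 1 and 2 (2.2.2) name no comparator: "Describe the effects of applying a personalized concurrent exercise prescription guide on cardiovascular risk factors" and "Describe the effects of applying a personalized concurrent exercise prescription guide on physical capacity".

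No section says which t-test or ANOVA term decides efficacy, or that any term is not to be read that way.

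**The concern.** The ANOVA is asked for within-group and between-group differences, but the plan does not match either question to a term. A reader looking for the within-group answer finds only one term that concerns change alone, Time, and Time is the average change over both arms. A reader looking for the between-group answer has three candidates: Group, Group × Time and the post-intervention t-test. They do not estimate the same quantity with the same precision.

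Two things are at stake. A change shared by both arms could be misread as benefit from the guide, more easily because specific objectives 1 and 2 do not mention the control group. And with the choice among three between-arm results left open, the chance of a false positive for a given variable exceeds the stated 5%, while a reader who relies on Group sees a halved effect.

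**Working it through.** **Inputs from the plan (2.3).** Two arms, 1:1; one pre and one post value; 15 per arm; type I error 5%; standardised effect 0.5.

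**Assumptions.** The documents give no pre-post correlation, so r = 0.5, 0.7 and 0.8 are used. They give no size for a change common to both arms, so 0.5 SD is used, with 0.3 SD as a milder case. Tests are two-sided, since sidedness is not stated. Data are normal with SD 1 at both times and complete for 15 per arm.

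**The plan's own figure.** An independent t-test with effect 0.5, 5% error and "Statistical power: 80"% needs 64 per arm two-sided (51 one-sided). With 15 per arm the power is 26% (38% one-sided). The section also cites recommendations for pilot studies, and this point does not depend on that figure.

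**What each term estimates.** Let m be the common expected baseline (equal by randomisation), c the change common to both arms and D the guide's effect. Expected means are m and m + c in the control group (CG), and m and m + c + D in the experimental group (EG).

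- Group = (2m + c + D)/2 − (2m + c)/2 = **D/2**
- Time = [(m + c) + (m + c + D)]/2 − m = **c + D/2**
- Group × Time = (c + D) − c = **D**

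The exercise arm's own change is c + D, which is not what Time estimates. If D = 0, Time equals c. These results do not depend on r.

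**Standard errors with n = 15 per arm, SD 1.**

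- Group: √((1 + r)/15) = 0.316, 0.337, 0.346
- Group × Time: √(4(1 − r)/15) = 0.365, 0.283, 0.231
- Post-only difference: √(2/15) = 0.365
- Baseline-adjusted difference (ANCOVA): about √(2(1 − r²)/15) = 0.316, 0.261, 0.219
- Time: √((1 − r)/15) = 0.183, 0.141, 0.115

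With D = 0.5, effect over standard error at r = 0.5 is 0.25/0.316 = 0.79 for Group, 0.5/0.365 = 1.37 for Group × Time and 0.5/0.316 = 1.58 for ANCOVA. For Time with c = 0.5 and D = 0 it is 0.5/0.183 = 2.74.

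**Share of trials significant** (40,000 simulated trials per setting; the Group, Group × Time and Time rates agree with the noncentral t distribution).

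| Setting | Result | r = 0.5 | r = 0.7 | r = 0.8 |
|---|---|---|---|---|
| D = 0.5, c = 0 | Group | 12% | 11% | 11% |
| | Post-only t-test | 26% | 26% | 26% |
| | Group × Time | 26% | 40% | 55% |
| | ANCOVA | 32% | 44% | 57% |
| D = 0, c = 0.5 | Time | 75% | 93% | 99% |
| | Group × Time | 5% | 5% | 5% |
| D = 0 | Any of Group, Group × Time, post-only | 11% | 11% | 11% |

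With a common shift of 0.3 SD and no guide effect, Time is significant in 36% of trials at r = 0.5 and 71% at r = 0.8. Simulated rates can differ by about a point between runs.

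**The case against.** The strongest reply is that the plan already contains the right contrast. Group × Time is in the model, and with two time points it is the t-test on change scores. Tukey's test is made conditional on it, which is the usual interaction-first reading. A non-significant interaction is itself a between-arm result. The post-intervention t-test and Cohen's d give further information on each variable. All of this stands.

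A reader might therefore infer too much in four ways.

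- *That the ANOVA cannot show what the guide did.* It can, through Group × Time.
- *That only main effects remain when there is no interaction.* The interaction estimate and the t-test remain.
- *That the Group main effect is invalid.* Under randomisation and no effect it rejects in 5% of trials; it is diluted, not wrong.
- *That a Time effect will be reported as benefit.* No section says so. The general objective and the hypotheses name the comparator, and controls are asked to keep their habits and medication unchanged. The 0.5 SD common shift is an assumption. Some shared change is possible, since activity counselling is given at programme check-ups (1.2) and the step test allows one attempt on the test day, with no practice test described, but the documents do not size it.

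What the reply does not supply is a statement of which result decides efficacy, or which term is meant to answer the within-group question.

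**Conclusion.** The point holds as a gap in specification. The plan includes a sound between-arm contrast but does not designate it, and leaves beside it a diluted test (Group), a post-only test that makes no use of the baseline, and a pooled term (Time) that answers neither stated question. That Group estimates half the effect and Time pools the arms is algebra, which holds whenever the arms are equal at baseline in expectation. The rates rest on 15 completers per arm and the assumed correlations; the Time rates rest also on the assumed shift. The figure of about 11% false positives applies to one variable if any of the three between-arm results may count as positive, before the number of primary variables is considered. The documents do not show that the main effects will be misused, so the risk is that they could be. Baseline adjustment also does somewhat better than Group × Time here, with the larger gain when the correlation is low (32% against 26% at r = 0.5; 57% against 55% at r = 0.8).

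**What to change.** In the Statistical Analysis part of section 2.3, replace the sentence on the purpose of the ANOVA with text such as: *For each variable, efficacy is judged on the difference between EG and CG at post-intervention adjusted for the baseline value (ANCOVA), reported as an estimate with a 95% confidence interval. Group and Time main effects are not evidence on efficacy. Within-arm changes are descriptive.* If Group × Time and the post-intervention t-test are kept, label them supportive.

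Reword specific objectives 1 and 2 to describe the difference between EG and CG, in line with the general objective.

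The cost is rewording the analysis text and two objectives. The adjusted analysis uses measurements already planned and needs no extra participants, visits or procedures. It should be settled before anyone sees results by arm.

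### Tukey's test after a Group x Time interaction adds nothing useful in a 2 x 2 pre-post design, and in its usual single-error form it misstates one set of standard errors; planned contrasts should replace it

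*Combined protocol and SAP*

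**What the plan says.** All of this is in section 2.3.

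- Assessments: "All evaluations will be conducted pre- and post-intervention in the experimental and control groups". There are two time points.
- Model: "A two-way repeated measures ANOVA will be used to determine intra-group and inter-group differences". Its terms are fixed: "Model effects will include Group (CG and EG), Time (Pre-test, Post-test), and their interaction over time".
- Follow-up: "Tukey's post hoc test will be used for variables with Group" x Time interaction. The plan does not say which means are compared, with what error term or with what degrees of freedom. It names the software but no procedure.
- Separately: "To identify group differences at baseline and post-intervention, the Student's t-test for independent samples will be used", with Levene's test alongside.

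The follow-up step therefore runs only for variables that pass the interaction test, and the ANOVA is meant to serve both within-arm and between-arm comparisons.

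**The concern.** Tukey's procedure compares three or more means that are independent and share one error variance. Here no factor has three levels, and the interaction is a single contrast with one degree of freedom, so nothing within it remains to be separated. If the procedure is run on the four cell means, two kinds of comparison are mixed. Means of different arms are independent, while pre and post means in one arm come from the same people and are correlated. One mean square cannot give both kinds the right standard error.

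At stake is the statement of where a difference lies, for each variable with an interaction. Depending on an error term that the plan leaves open, the same data could miss a real change in the exercise arm, or show a baseline difference between randomised arms that is not there.

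**Working it through.** **Inputs.** Two groups, two times, 15 per arm (section 2.3, Sample Size Calculation), and an effect of 0.5 SD ("Effect size (ES): 0.5 according to Cohen's classification"). The documents give no pre-post correlation rho, so 0.5, 0.7 and 0.8 are assumed. The plan states no figure for the post hoc step, so there is none to reproduce.

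**1. What Tukey can act on.**
- Within a two-level factor: q(0.05; 2, 28)/sqrt(2) = 2.048, and t(0.975, 28) = 2.048. It is the t-test and adjusts nothing.
- On the four cells there are 4 x 3/2 = 6 comparisons. Two of them (control-pre against exercise-post, control-post against exercise-pre) differ in both arm and time and answer no question. The multiplier is q(0.05; 4, 28)/sqrt(2) = 3.861/1.414 = 2.73, or 2.65 with 56 df.

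**2. True standard errors, with equal variances sigma^2.**
- Between arms at one time: sqrt(2 sigma^2/n) = sqrt(2/15) = 0.365 SD.
- Within an arm, post minus pre: sqrt(2 sigma^2 (1 - rho)/n) = 0.258/0.200/0.163 SD at rho 0.5/0.7/0.8.

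The two are equal only if rho = 0.

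**3. What one mean square does.**

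| Error term | Estimates | Between-arm SE / true SE | Within-arm SE / true SE |
|---|---|---|---|
| Within-subject | sigma^2 (1 - rho) | sqrt(1 - rho) = 0.71/0.55/0.45 | 1 |
| Pooled over cells | sigma^2 | 1 | 1/sqrt(1 - rho) = 1.41/1.83/2.24 |
| Between-subject | sigma^2 (1 + rho) | sqrt(1 + rho) = 1.22/1.30/1.34 | sqrt((1 + rho)/(1 - rho)) = 1.73/2.38/3.00 |

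Each choice leaves at least one set wrong.

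**4. Size of change needed to be flagged.** With the pooled error and 56 df, a within-arm change must exceed about 2.65 x 0.365 = 0.97 SD whatever rho is, against a true change of 0.5 SD. Tukey with the within-subject error needs 2.73 x the true standard error = 0.70/0.55/0.45 SD.

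**5. Simulation.** 15 per arm, normal data, true exercise effect of 0.5 SD at post. Percentages are of trials with a significant interaction, since only then does the plan run Tukey. Repeat runs differ by about one percentage point.

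| Result | rho 0.5 | rho 0.7 | rho 0.8 |
|---|---|---|---|
| Real exercise-arm change flagged: Tukey, pooled error, 56 df | 15% | 5% | 2% |
| The same with 28 df | 13% | 4% | 1% |
| Tukey, within-subject error, 28 df | 59% | 74% | 85% |
| Unadjusted paired contrast | 82% | 90% | 96% |
| Baseline arm difference (truly zero) flagged: Tukey, within-subject error | 10% | 17% | 24% |

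The step from the first row to the third is due almost wholly to the wrong standard error. The step from the third to the fourth is mainly the price of adjusting for six comparisons. As a benchmark for the last row, the per-comparison rate with a correct standard error and the 2.73 multiplier is about 1% over all trials.

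**The case against.** The strongest reply is that the plan names a test and no more. A reader might infer that the follow-up comparisons must carry wrong standard errors. The text does not support that. Tukey multipliers with a separate standard error for each comparison are valid at every rho, and Tukey within a two-level factor is redundant but harmless. The wrong standard error follows from one standard way of running the test, which the plan neither selects nor rules out.

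A reader might also infer that the efficacy result is compromised. It is not. The Group x Time test has one degree of freedom and is complete before Tukey begins. The independent-samples t-tests at baseline and post-intervention carry the correct between-arm standard error.

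Nor is the false baseline flag an error rate for the trial as a whole. With the within-subject error, the chance of both reaching Tukey and flagging baseline is about 2.5/6.7/13.4% at rho 0.5/0.7/0.8 when the effect is real, and about 1.2/1.5/1.8% when the arms do not differ.

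These limits stand, but they do not rescue the step. The t-tests already cover the between-arm comparisons, so Tukey's only distinct use is the within-arm change, which is where the pooled error nearly always fails. With the within-subject error, Tukey can contradict the t-test on the same contrast, and the plan has no rule for which prevails. Even the valid version loses power to comparisons that nobody wants.

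**Conclusion.** The point holds as a poor choice of method with a cheap, better replacement. In this design Tukey's test is either the t-test under another name or a six-comparison procedure on four means. In its classical single-mean-square form, the latter misstates one set of standard errors by a factor of 1.41 to 2.24 (pooled, too wide) or 0.71 to 0.45 (within-subject, too narrow) over rho 0.5 to 0.8. The harm is limited to the follow-up statements; the interaction test and the between-arm t-tests are untouched. The sizes rest on 15 completers per arm, equal variances, normal data, a true effect of 0.5 SD and an assumed rho. The existence of the mismatch rests only on rho not being zero.

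**What to change.** Delete the Tukey sentence. In its place, state that for every variable, whether or not the interaction is significant, the report will give:

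- the between-arm difference in change (the Group x Time contrast) with its 95% CI, as the efficacy estimate; a baseline-adjusted difference could serve instead, but no model in the plan has a baseline covariate, so that model would have to be added;
- each arm's mean change with a paired 95% CI, labelled descriptive;
- no comparisons across both arm and time.

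The cost is one sentence and a few extra intervals from data already being collected. The within-arm changes are then not adjusted for multiplicity, which is why they should be labelled descriptive and not used to claim efficacy.
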